[name]
[name]
[name]
USA
www.medtronic.com

Official Title: A Post-market Feasibility Study Evaluating Location Accuracy Using the superDimension™ Navigation System Version 7.2 With Fluoroscopic Navigation Technology in Subjects Undergoing Lung Lesion Biopsy

ClinicalTrials.gov ID: NCT03585959

Date of Document: 05Dec2019

Note to File Fluoroscopic Navigation Study

GBET-091

v2

Page 1 of 2

Global
Business
Efficiency
Tool
Medtronic

Note to File

Study name:	MDT18004ILSFNV (Fluoroscopic Navigation Clinical Study)	Investigation Site Name/ Number (if applicable):	N/A
Subject:	Fluoroscopic Navigation Clinical Study Inclusion/Exclusion Criteria CIP Typos		

Prepared by	[name]
Date of preparation	20 Nov 2019
Document	Fluoroscopic Navigation CIP_Final_v1.0_09Apr18

This Note to File is to document typos in the inclusion and exclusion criteria of the Clinical Investigation Plan (CIP) for the Fluoroscopic Navigation Clinical Study.

On 18Sep19 the ILS Medical Writer identified a typo in the CIP for the Fluoroscopic Navigation Clinical Study regarding the Exclusion Criteria 1. The word "not" was included in error:

Central lesions that are **not** visible endobronchially or could be reached by a flexible bronchoscope or endobronchial ultrasound (EBUS) without utilization of ENB

Exclusion Criteria 1 should have stated: *re [name] 5Dec2019*

Central lesions that are **not** visible endobronchially or could be reached by a flexible bronchoscope or endobronchial ultrasound (EBUS) without utilization of ENB

On 29Oct19, a site Principal Investigator noticed that Inclusion Criteria 1 inaccurately states the targeted lesion size for potential subjects:

Subjects presents with lung lesion(s) greater than 10 mm in diameter amendable to evaluation by the ENB at the time of the evaluation

Inclusion Criteria 1 should have stated:

Note to File Fluoroscopic Navigation Study

GBET-091

[figure not shown]
v2

Page 2 of 2

Global
Business
Efficiency
Tool
Medtronic

Subjects presents with lung lesion(s) greater than **or equal to** 10 mm in diameter amendable to evaluation by the ENB at the time of the evaluation

The intent of the inclusion criteria was to be consistent with the superDimension Indications for Use.

The CIP will not be updated as the study has been closed by the sponsor and the Site IRBs.

Name: [name]	Role: Clinical Study Manager
Signature:	Date: 12/01/2019 (dd/mmm/yyyy)

Approved by:

## 1. Version History

Version	Summary of Changes	Author(s)/Title
1.0	
 
• New Document
 
	[name], Statistician
1.1	
 
• Revise the “Figure 1. Procedure Steps”
 
	[name], Statistician
1.2	
 
• Revise “Figure 1” and the secondary endpoint
 
	[name], Statistician

## 2. List of Abbreviations and Definitions of Terms

Abbreviation	Definition
AE	adverse event
AP	anteroposterior
CBCT	cone-beam computed tomography
CIP	clinical investigation plan
CT	computed tomography
CTCAE	Common Terminology Criteria for Adverse Events
EC	Ethics Committee
ENB	electromagnetic navigation bronchoscopy
eCRF	electronic case report form
EWC	extended working channel
FDA	Food and Drug Administration
GCP	good clinical practice
ICF	informed consent form
ICH	International Conference on Harmonisation
IFU	instructions for use
ILS	Medtronic Interventional Lung Solutions
IRB	institutional review board
LG	locatable guide

Abbreviation	Definition
MDR	medical device reporting
ROSE	rapid on-site evaluation
SAE	serious adverse event
SAP	statistical analysis plan

### 3. Introduction

This is a post-market feasibility study evaluating location accuracy using the superDimension™ Navigation System Version 7.2 with Fluoroscopic Navigation Technology in subjects undergoing lung lesion biopsy.

This document provides a detailed description of the statistical methods and procedures to be implemented during the analysis of the study.

This statistical analysis plan (SAP) is based on the CIP version 1.0 dated on 09APR2018.

### 4. Study Objectives

The primary objective of this post-market feasibility study is to confirm the location accuracy of the local registration feature of the superDimension™ navigation system v7.2 in subjects undergoing lung lesion biopsy.

### 5. Investigation Plan

This post-market feasibility study is planned in up to 50 subjects meeting the inclusion criteria and undergoing elective ENB with the superDimension™ Navigation System v7.2 with Fluoroscopic Navigation Technology. The study will confirm the location accuracy of the optional local registration feature. Enrolled subjects will first undergo a standard ENB procedure to navigate to within 2.5 cm of the target lesion. Local registration with Fluoroscopic Navigation Technology will be conducted and fluoroscopy and CBCT scans will be used to document that the biopsy tool location accuracy.

Periprocedural endpoints include confirmation of accurate positioning of the virtual target (representing the target lesion), technical success, relational accuracy, adequate periprocedural location, procedure time, adequacy of tissue captures for pathology, tool usage, and histopathological results. Safety will be evaluated immediately post-procedure and 4-7 days post-procedure.

This study will be conducted in subjects over the age of 18 undergoing elective biopsy of lung lesions greater than 10 mm in diameter. Additional inclusion/exclusion criteria are listed in CIP section 8.3 and 8.4.

# [Fluoroscopic Navigation] Statistical Analysis Plan

MDT18004ILSFNV

Revision [1.0]

Page 5 of 10

Form

Medtronic

The overview of procedure (Figure 1):

[figure not shown]

Figure 1. Procedure Steps

## 6. Determination of Sample Size

This study will enroll up to 50 subjects meeting the inclusion criteria, with a maximum of 25 subjects per site. The sample size of this feasibility study is not based on power calculations of a statistical hypothesis test.

## 7. Statistical Methods

### 7.1 Study Subjects

#### 7.1.1 Disposition of Subjects

Variables to be collected, follow-up visit schedule, and tests to be performed at each visit are described in **Table 1** below.

**Table 1.** Schedule of Events

	Baseline (Day - 30 to Day 0)	During and immediately post- procedure (Day 0)	7 days Post- Procedure (window = 4-7 days)
Informed consent	X		
Eligibility criteria	X		
Demographics	X		
Medical history	X		
Procedural information		X	
Lesion characteristics	X	X	
Adverse event assessment		X	X
Biopsy results		X	X

Subject disposition (e.g., number of subjects enrolled, number of subjects completing the study) will be summarized with frequency tables.

#### 7.1.2 Clinical Investigation Plan (CIP) Deviations

Deviations are instance(s) of failure to follow, intentionally or unintentionally, the requirements of the CIP. All deviations must be documented and explained, regardless of the reason for the deviation.

The total number of protocol deviations and total number of subjects with deviations will be provided by deviation type for all enrolled subjects. Number of protocol deviations and number of subjects with deviations by each investigational site will also be provided.

### 7.1.3 Analysis Sets

- Enrolled subjects

Subjects meeting the inclusion/exclusion criteria will be enrolled. Following signing the informed consent form (ICF), the point of enrollment is defined as the entry of the first locatable guide.

- Technically Successful cases

Successful completion of Local Registration utilizing Fluoroscopic Navigation Technology in superDimension™ Navigation System Version 7.2.

The following study endpoints will be evaluated in Technically Successful cases:

- Primary endpoint
- Secondary endpoints:
  - Percentage of cases in which the intended lesion is correctly identified (as opposed to a non-target lesion or normal lung tissue) as indicated by the system software.
  - Relational Accuracy in cases in which the Intended lesion is targeted.

All other endpoints and safety outcomes will be evaluated in all enrolled subjects.

## 7.2 General Methodology

All statistical analyses will be performed using Statistical Analysis System (SAS) for Windows (version 9.2 or higher, SAS Institute Inc. Cary, NC) or other widely accepted statistical or graphical software.

Descriptive statistics will be used to present the data and to summarize the results. Continuous variables will be summarized with number of subjects (n), mean, standard deviation, median, and ranges.

Categorical variables will be summarized by frequencies and percentages.

## 7.3 Center Pooling

This is a multi-center clinical study, with standardization of subject enrollment, data entry and adverse event reporting. All the data will be pooled for reporting.

## 7.4 Handling of Missing, Unused, and Spurious Data and Dropouts

Due to the post-market and observational nature of the study, no imputation is planned for missing data in the primary and secondary endpoints, if any. All available data from enrolled subjects will be reported.

## 7.5 Adjustments for Multiple Comparisons

No multiple comparisons/multiplicity adjustments will be made.

## 7.6 Demographic and Other Baseline Characteristics

Baseline, demographic and medical history data will be collected for all enrolled participants. These characteristics will be summarized using descriptive statistics.

## 7.7 Treatment Characteristics

- Procedure Characteristics

The subject-based procedure characteristics will be summarized using descriptive statistics.

- Lesion Characteristics

The lesion-based characteristics will be summarized using descriptive statistics.

## 7.8 Evaluation of Objectives

### 7.8.1 Primary Endpoint

The Primary Endpoint is the measured ability of the superDimension™ Navigation System v7.2 with Fluoroscopic Navigation Technology to place the center of the virtual navigation target (green ball) on the intended target lesion as confirmed by CBCT.

The primary endpoint will be evaluated in Technically Successful cases (local registration complete) and calculated as the number and percentage of cases in which the center of the virtual target was correctly placed to overlap the target lesion in coronal view, as confirmed by CBCT. In 'MUO\_IMAG' CRF, the subject meets the primary endpoint if 'Target Overlap in Coronal View' is checked 'Yes'.

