In ‘DIAG’ CRF, ‘Tool Name’, ‘Tool Order’ and ‘Number of Passes’ will be summarized using the descriptive statistics or data listing.

In Technically Successful cases (local registration complete):

- Percentage of cases in which the intended lesion is correctly identified (as opposed to a nontarget lesion or normal lung tissue) as indicated by the system software.

In MUO CRFs, 'Was the target/planned lesion correctly marked by the physician?' will be summarized using the descriptive statistics to present the count and percentage.

- Relational Accuracy in cases in which the Intended lesion is targeted.

Relational accuracy, defined per protocol as the three-dimensional relationship between the catheter and the lesion in terms of distance and vector, was calculated as the three-dimensional percentage overlap between the virtual target and the actual lesion in CBCT.

In MUO CRFs, 'Calculated Percent Overlap' will be summarized using descriptive statistics.

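### Does scoring the primary endpoint from one coronal view, without naming the slice, leave location accuracy untested in the anteroposterior direction?

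*SAP*

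**What the plan says.** SAP 7.8.1 describes the primary endpoint as the measured ability of the system to "place the center of the virtual navigation target (green ball) on the intended target lesion as confirmed by CBCT". That description names no plane. The calculation that follows is the number and percentage of technically successful cases in which "the center of the virtual target was correctly placed to overlap the target lesion in coronal view, as confirmed by CBCT". Scoring comes from one yes/no CRF item: "the subject meets the primary endpoint if 'Target Overlap in Coronal View' is checked 'Yes".

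Three other parts of the SAP bear on this:

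- Section 4 gives the objective, which is to "confirm the location accuracy of the local registration feature".
- Section 7.1.3 restricts the primary endpoint and two secondary endpoints to one subset: "The following study endpoints will be evaluated in Technically Successful cases".
- Section 7.8.2 plans "Relational Accuracy in cases in which the Intended lesion is targeted", a quantity that "was calculated as the three-dimensional percentage overlap between the virtual target and the actual lesion in CBCT".

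Section 6 allows up to 50 subjects and says that this number does not come from a power calculation. Section 3 ties the SAP to its parent document: "This statistical analysis plan (SAP) is based on the CIP version 1.0". The body of that clinical investigation plan, the CRF instructions and the SAP's Figure 1 are not available here.

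**The concern.** The description is three-dimensional (a center on a lesion), while the score comes from a two-dimensional view. The SAP does not say which coronal image is read. If it is a projection, or a slice fixed on the lesion whatever the depth of the target, a target in front of or behind the lesion could still be scored as a success. The percentage would then overstate how often the center lies inside the lesion. The CRF label adds to the doubt because it mentions overlap without mentioning the center.

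This percentage is the only primary result and carries the single stated objective. Because the study is descriptive, the reported number is in effect the conclusion, so what it measures matters.

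**Working it through.** The plan has no figure to reproduce: it gives no alpha, power, expected rate or threshold. The check is therefore geometric, followed by an illustration on assumed inputs.

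**1. What each reading measures.** Let the target center be at (x, y, z), with z the anteroposterior coordinate, and let L be the lesion volume.

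- *Coronal slice through the target center.* The lesion outline on that slice is the set of points (a, b) for which (a, b, z) is in L. The center falls inside the outline exactly when (x, y, z) is in L. The coronal answer is three-dimensional containment, for any lesion shape and any error distribution. Gap: 0.
- *Projection.* The center scores if (x, y) lies under any part of L. This is a weaker condition, so the rate is equal to or higher than three-dimensional containment.
- *Slice fixed through the lesion center.* For a sphere this gives the same result as the projection.

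**2. Size if a projection were read.** Assumptions not in the documents: spherical lesion of radius R; Gaussian error centered on the lesion with SD s on each axis; diameters of 10, 20 and 30 mm (the SAP gives only a lower limit of 10 mm). With u = R/s:

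- Projection: 1 − exp(−u²/2)
- Three-dimensional containment: chi-square CDF with 3 df at u², which equals 2Φ(u) − 1 − √(2/π)·u·exp(−u²/2)

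For a 20 mm lesion and s = 5 mm, u = 2. Projection: 1 − exp(−2) = 86.5%. Containment: 0.9545 − 0.7979 × 2 × 0.1353 = 73.9%. Gap: 12.6 points.

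| Diameter (s = 5 mm) | Projection | 3D containment | Gap (points) |
|---|---|---|---|
| 10 mm | 39.3% | 19.9% | 19.4 |
| 20 mm | 86.5% | 73.9% | 12.6 |
| 30 mm | 98.9% | 97.1% | 1.8 |

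The largest gap under these assumptions is 21.0 points, at u = 1.25. If the anteroposterior SD is assumed to be twice the in-plane SD, containment for the 20 mm lesion falls to 48.5% and the gap is 38.0 points.

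If all 50 subjects are evaluable with one lesion each, 12.6 points is 0.126 × 50 = 6.3 cases. For scale, 37 of 50 has an exact 95% interval of 59.7 to 85.4%, a half-width of (85.4 − 59.7)/2 = 12.9 points.

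**3. What the planned overlap already shows.** For two equal spheres of radius R with centers a distance d apart, the shared fraction is (4R + d)(2R − d)²/(16R³). With the center on the lesion boundary, d = R, this is 5R·R²/(16R³) = 31.25%. It falls steadily as d grows. With equal spheres, overlap above 31.25% therefore means that the center is inside.

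The conversion fails if the target ball is smaller than the lesion. For lesions of 10 to 30 mm and assumed balls of 5 to 10 mm, a center on the boundary corresponds to 31.3 to 46.9% of the ball volume, or 0.2 to 31.3% of the lesion volume. SAP 5 says that the virtual target represents the lesion but gives no size, and 7.8.2 does not name the denominator volume.

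**4. Which reading the text supports.** The calculation sentence in 7.8.1 names the center and the CBCT. A CBCT is a volume that is read in slices, and judging a center on it naturally means going to the slice that contains that center. No section mentions a projection or a slice chosen without regard to the target. The same sentence settles the CRF label: the overlap in question is that of the center.

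**The case for a change.** The strongest case for a change is that the SAP should stand on its own for its only primary result. Its text does not fix the reading, and under a projection the overstatement could be as large as the sampling error. Percent overlap does not replace a center-in-lesion result: it has no threshold, its denominator volume is not stated, and it covers only cases in which the intended lesion is targeted. A clarifying sentence and one more descriptive row, for at most 50 subjects and without new imaging, would cost little.

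Part of this stands. The slice is not named in the SAP, the arithmetic is right, and percent overlap cannot in general be turned into center containment. The case for changing the plan is weaker:

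- All of the gap comes from readings that the documents do not suggest. On the direct reading it is 0, and an added three-dimensional row would repeat the primary result.
- That row needs stored center coordinates or lesion volumes, and the documents do not say that either was kept.
- The Note to File reports the study closed, and SAP 7.8.2 already describes the overlap calculation in the past tense. A slice rule written into 7.8.1 now could differ from what the readers did.
- A gap in the SAP is not shown to be a gap in the study, because the reading rule may sit in the clinical investigation plan, the CRF instructions or Figure 1.

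**Conclusion.** No change to the plan. SAP 7.8.1 leaves out a reading detail, but following it in the ordinary way, on the CBCT coronal slice that contains the target center, gives three-dimensional center containment with no error. That equality needs no assumption about lesion shape or placement error.

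The illustrative gaps of up to 21.0 points (38.0 in the 20 mm example with doubled anteroposterior error) arise only if a projection or a lesion-fixed slice was read. They also rest on assumed spherical lesions and assumed error SDs, so they do not estimate any effect in this study. With no hypothesis test and no success threshold, no decision would change either way.

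Naming the view that was read is a normal detail of the clinical study report. Only if it was not the slice through the target center would the primary percentage need a caution that anteroposterior position was not fully tested, with the planned overlap result beside it. Confidence is moderate, because the documents most likely to hold the reading rule are not available here.

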### 7.8.2 Secondary Endpoints

The following secondary endpoints will be evaluated in all enrolled subjects:

- Number of cases that are technically successful (successful completion of local registration), define as,
  - In 'LESN\_CHAR' CRFThe technically successful is defined as that 'Was local registration successful' is checked 'YES'. The results will be summarized using frequency measures in the format of p% (x/N), with x being the number of lesions with successful completion of local registration and N being the number of lesions undergo the procedure.
- In cases that are not technically successful, reason for incomplete local registration in each target lesion, define as,
  - In 'LESN\_CHAR' CRFIf 'Was local registration successful' is checked 'NO', list all detail from 'If No, provide reason'.

- Investigator confirmation that the catheter is in an “Adequate Periprocedural Location” (the location of the extended working channel with the proceduralist makes the decision that placement is adequate and clinically acceptable to proceed with tissue sampling), define as,
  - In ‘LESN\_CHAR’ CRF

If ‘Adequate Periprocedural Location’ is checked ‘YES’. The results will be summarized using frequency measures in the format of p% (x/N), with N being the number of lesions undergoing the procedure.

- Total procedure time, define as,

In ‘PROC’ CRF, first entry of the bronchoscope to the last exit of the bronchoscope

- ENB procedure time, define as,

In ‘PROC’ CRF, total time from the first entry of the extended working channel or locatable guide until the last exit of the extended working channel.

- Total fluoroscopy time, as measured by the fluoroscopy system, define as,

In ‘PROC’ CRF, ‘What was the total fluoroscopic time’ will be summarized using the descriptive statistics.

- Adequacy of the ENB-aided tissue sample for rapid on-site evaluation (ROSE) of cytologic samples by pathology (when applicable)

In ‘DIAG’ CRF, if ‘ROSE Diagnosis’ is not checked ‘INADEQUATE TISSUE FOR ROSE’.

- Histopathological call based on ROSE of the ENB-aided tissue sample (when applicable)

In ‘DIAG’ CRF, ‘ROSE Diagnosis’ will be summarized using the descriptive statistics of categorical variables.

- Final pathology results of the ENB-aided tissue sample

In ‘DIAG’ CRF, ‘Pathology Diagnosis’ will be summarized using the descriptive statistics of categorical variables.

- Biopsy tools used, tool order, number of passes, and final pathology of the ENB-aided sample

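### Does the primary endpoint divide subjects by lesions, and is an accuracy rate over all lesions missing?

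*SAP*

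**What the plan says.** SAP 7.8.1 sets the population: "The primary endpoint will be evaluated in Technically Successful cases (local registration complete"). The rate is "calculated as the number and percentage of cases in which the center of the virtual target was correctly placed" on the lesion in coronal view, as shown by CBCT. The next sentence links this to the MUO_IMAG form: "the subject meets the primary endpoint if" the coronal-overlap item is marked Yes.

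SAP 7.8.2 opens with "The following secondary endpoints will be evaluated in all enrolled subjects". Its first item is "Number of cases that are technically successful (successful completion of local registration"), reported as p% (x/N), "with x being the number of lesions with successful completion of local registration and N being the number of lesions undergo the procedure". For failures it lists the "reason for incomplete local registration in each target lesion".

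Other relevant places:
- SAP 7.1.3 defines the Technically Successful set by completed local registration and does not say whether a member is a subject or a lesion.
- SAP 7.7 summarises procedure characteristics by subject and lesion characteristics by lesion.
- The Note to File in the Protocol document cites inclusion criterion 1: "Subjects presents with lung lesion(s) greater than 10 mm in diameter amendable to evaluation by the ENB".
- SAP 5 and 7.8.1 speak of the target lesion in the singular.
- SAP 4 gives the objective as confirming the accuracy of local registration.
- SAP 6 caps enrolment at 50 subjects and states that no power calculation was made.

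**The concern.** Two things look wrong at first.

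The first is the unit. The primary rate is over cases, the sentence that scores it names the subject, and the neighbouring section treats technically successful cases as lesions. Read literally and together, a count of subjects could be placed over a count of lesions. Such a ratio cannot reach 100% once anyone has two target lesions. No supplied text says how to score a subject with one lesion on target and one off, or one registered and one not.

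The second is the denominator. The primary endpoint and both secondary accuracy endpoints (correct identification and relational accuracy) are confined to completed registrations. The location measure that uses all lesions, Adequate Periprocedural Location, is the investigator's judgement of catheter position and not CBCT-confirmed overlap. A reader could take the conditional percentage for the chance of accurate placement in every lesion attempted.

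In a descriptive study the headline percentage is the main result, so its meaning is what would be at stake.

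**Working it through.** The plan states no rate to reproduce. The only design figure used is the cap of 50 subjects (SAP 6). The counts of two-lesion subjects, the accuracy and the registration failures below are all assumptions.

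**1. Is a mixed ratio planned?** The sentence in 7.8.1 that defines the rate uses one noun, cases, for both the number and the percentage. The sentence with the word subject says which tick-box counts as success and sets no denominator. The lesion N belongs to items in 7.8.2 recorded on a different form, LESN_CHAR. A subjects-over-lesions rate needs a numerator from one section and a denominator from the other, and no section asks for it. The lead-in to 7.8.2 is not a second conflict: it names a population, within which lesions are counted.

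**2. How much does the choice between consistent units matter?** Let s be the share of subjects with two lesions and p the accuracy per lesion, with lesions independent and all registered.

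- Lesions over lesions: p
- Subjects, any lesion on target: (1 − s)p + s[1 − (1 − p)²]
- Subjects, all lesions on target: (1 − s)p + sp²
- Subjects, index lesion only: p

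With p = 0.90, 1 − (0.10)² = 0.99 and 0.90² = 0.81:

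| Two-lesion subjects of 50 | By lesion | Any | All | Index |
|---|---|---|---|---|
| 0 (s = 0) | 90.0% | 90.0% | 90.0% | 90.0% |
| 5 (s = 0.1) | 90.0% | 90.9% | 89.1% | 90.0% |
| 10 (s = 0.2) | 90.0% | 91.8% | 88.2% | 90.0% |

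The shift in either direction is s·p(1 − p) = 0.2 × 0.09 = 1.8 points at most in this table. One binomial standard error is √(0.9 × 0.1/50) = 4.2 points. Since p(1 − p) never exceeds 0.25, the shift at s = 0.2 cannot exceed 0.2 × 0.25 = 5.0 points at any accuracy, under the same independence assumption.

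**3. Extreme case.** Suppose all 10 two-lesion subjects have one hit and one miss, and every other lesion is a hit. The lesion rate is 50/60 = 83.3%, the any rule gives 50/50 = 100% and the all rule gives 40/50 = 80.0%. Under independence at p = 0.90, the expected number of such subjects is 10 × 2 × 0.9 × 0.1 = 1.8, not 10.

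**4. Conditional rate against all lesions.** Take one lesion per subject, N = 50 and complete CBCT:

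| Failed registrations | Conditional | Over all lesions | Gap (points) |
|---|---|---|---|
| 0 | 45/50 = 90.0% | 45/50 = 90.0% | 0 |
| 1 | 44/49 = 89.8% | 44/50 = 88.0% | 1.8 |
| 3 | 42/47 = 89.4% | 42/50 = 84.0% | 5.4 |
| 5 | 40/45 = 88.9% | 40/50 = 80.0% | 8.9 |
| 10 | 36/40 = 90.0% | 36/50 = 72.0% | 18.0 |

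The gap can be large, but it is not hidden. Technical success is planned as registered/N, and the primary rate as accurate/registered. Their product is accurate/N. With 5 failures, 45/50 × 40/45 = 40/50 = 80.0%.

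**The case for a change.** The best case for a change is that the tick-box sentence is the programming rule for the headline result, so its unit should be fixed, and that doing so takes one word. The two parts also compound. If the printed count is of subjects and some have several lesions, the all-lesion rate can no longer be derived exactly. For example, if 45 of 50 subjects are scored as met and 5 subjects have two lesions, between 45 and 50 lesions are on target, so the lesion rate lies anywhere from 45/55 = 81.8% to 50/55 = 90.9%.

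Part of this stands. Case is undefined in the supplied text, 7.1.3 names no unit, and there is no rule for a subject with several lesions.

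Three things limit it. First, the body of the CIP and the forms are not among the documents, so a one-lesion rule or a definition of case may exist there. The plural in the inclusion criterion describes how subjects present, not how many lesions are navigated. Second, replacing subject with lesion is correct only if MUO_IMAG is completed once per lesion, which the documents do not say, so a blind edit could bring in an error. Third, the planned tables already expose the problem if it arises. The number of enrolled subjects (7.1.1) set beside the lesion N (7.8.2) shows whether there are more lesions than subjects.

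On the denominator, a companion row would be convenient. It answers a different question, however: registration success and accuracy combined.

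**Conclusion.** No change to the plan follows. The unit point is an undefined word that an analyst would resolve by keeping one unit in numerator and denominator. It has no effect with one lesion per subject. It is worth at most 1.8 points with 10 two-lesion subjects of 50, assuming 90% accuracy and independent lesions. Only the contrived case in which every two-lesion subject is discordant gives a large shift (100% or 80.0% against 83.3%).

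The restriction to completed registrations is a declared choice, made in both 7.1.3 and 7.8.1, and it suits an objective about the registration feature itself. Failures are reported with reasons and with the all-lesion N, so the broader rate is one multiplication away when units match and CBCT is complete. Its absence as a printed row is not an error.

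The study has no hypothesis test, threshold or decision rule that either point could alter. The conclusion rests on the supplied text alone. It would need another look if the full CIP or the forms showed many subjects with several navigated lesions and a form completed only once per subject.
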